14.2. Sample Size/Accrual Rate

A total of 30 patients are to be enrolled, to allow at least 20 transplants for adequate primary endpoint analysis.

During immunotherapy, grade 3-5 AEs will be monitored. In the pivotal study of durvalumab and tremelimumab (Kelley et al, Abstract 4508 at ASCO 2020), 16% had Tx related (TR) SAEs, and 11% had discontinuation of treatment due to TR AEs. We will use these guardrails for interim safety analyses at 10 patients. We will pause enrollment and assess safety in detail to determine if the study should continue, in discussion with AstraZeneca if:

- Of the first 10 patients, if ≥ 3 patients have to discontinue immunotherapy due to treatment related AEs and/or;
- Of the first 10, if ≥ 3 patients experience SAEs related to locoregional therapy after immunotherapy and/or;
- Of the first 10, if ≥ 3 patients fail to reach liver transplant due to immunotherapy toxicity and/or;
- Of the first 10 patients, if ≥ 3 deaths are encountered, from enrollment to up to 30 days after transplant.

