10.4. Interim Safety Analysis

During immunotherapy, grade 3-5 AEs will be monitored and at 10 patients enrolled an interim safety analysis will be performed. We will halt enrollment and assess safety in detail to determine if the study should continue, in discussion with AstraZeneca if:

- Of the first 10 patients, if ≥ 3 patients have to discontinue immunotherapy due to treatment related AEs and/or
- Of the first 10, if ≥ 3 patients experience SAEs related to locoregional therapy after immunotherapy and/or
- Of the first 10, if ≥ 3 patients fail to reach liver transplant due to immunotherapy toxicity and/or
- Of the first 10 patients, if ≥ 3 deaths are encountered, from enrollment to up to 30 days after transplant

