12.2. Dose Limiting Toxicities

The DLT assessment period is from the time of first dose of IP and ends upon administration of the first dose of IP on Cycle 2, Day 1 (28-day cycle).

Any treatment-related toxicities that first occurred during the DLT period must be followed for resolution to determine if the event qualifies as a DLT.

A DLT is defined as the occurrence of an adverse event (AE) that is **at least possibly related to the investigational product (IP) or investigational regimen (IR)**, with two exceptions: any grade of vitiligo or alopecia will not qualify as a DLT. AEs that are **at least possibly related to durvalumab- and/or tremelimumab-containing regimens** shall be assessed as DLTs if they meet known toxicity criteria.

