15.4. Known Risks of Durvalumab + Tremelimumab

The safety of durvalumab + tremelimumab combination therapy was initially evaluated in the

ongoing dose escalation and dose expansion Study 006, in patients with NSCLC, and is being studied in a number of other ongoing clinical trials, in a number of different indications, and has to date shown a manageable safety and tolerability profile.

The types of risks with the combination of durvalumab + tremelimumab (based on an equivalent durvalumab dose of 20mg/kg and a tremelimumab dose of 1mg/kg) are similar to those for durvalumab and tremelimumab monotherapy. Emerging data from study 006, other studies evaluating the combination, and from combinations of other agents in the same class indicate an increased frequency and/or severity of some of these immune-mediated toxicities. For information on all identified and potential risks with the durvalumab+tremelimumab combination please always refer to the current version of the durvalumab IB.

In durvalumab+tremelimumab combination studies at the dose of durvalumab 20mg/kg and tremelimumab 1mg/kg AEs (all grades) reported very commonly ($\geq 15\%$ of patients) are diarrhoea, fatigue, decreased appetite, nausea, pruritus, constipation, and anaemia; AEs reported in $\geq 5\%$ of patients that were considered by the investigator as treatment-related were diarrhoea, pruritus, fatigue, rash, hypothyroidism, decreased appetite, nausea, asthenia, and hyperthyroidism. Known risks of combination therapy includes amylase increased, lipase increased, pancreatitis and noninfective encephalitis. Potential risks of the combination treatment include pulmonary embolism and subcutaneous injection site reaction. Approximately 17% of patients experienced an AE that resulted in permanent discontinuation of study drug and approximately 18% of patients experienced an SAE that was considered to be related to durvalumab and tremelimumab by the study investigator. A detailed summary of durvalumab + tremelimumab combination AE data can be found in the current version of the durvalumab IB.

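### The 16% treatment-related SAE benchmark named for the interim look has no matching pause rule, so immunotherapy-related SAEs go uncounted unless they lead to discontinuation, a missed transplant or death

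*Combined protocol and SAP*

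**What the plan says.** Section 14.2 (Sample Size/Accrual Rate) cites a study of the same drug combination and adopts its rates for a look at 10 patients: "16% had Tx related (TR) SAEs, and 11% had discontinuation of treatment due to TR AEs. We will use these guardrails for interim safety analyses". Four triggers for pausing enrolment follow, each set at 3 or more of the first 10 patients:

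1. Discontinuation: "if ≥ 3 patients have to discontinue immunotherapy due to treatment related AEs".
2. Locoregional SAEs: "if ≥ 3 patients experience SAEs related to locoregional therapy after immunotherapy".
3. Failure to reach transplant because of immunotherapy toxicity.
4. Death between enrolment and 30 days after transplant.

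Section 10.4 (Interim Safety Analysis) repeats the same four. Both sections say that grade 3-5 adverse events will be monitored during immunotherapy, but give no threshold for them.

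Outside these rules, the Synopsis (Study Design) lets the DSMB, the investigators, the sponsor-investigator and the drug manufacturer consider modifying or stopping the study on untoward safety signals. Section 15.14 sends SAEs to the DSMB. Section 17.3 gives the board summaries of adverse-event frequency and severity and makes its role advisory.

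**The concern.** The plan names two benchmarks and turns one into a rule. The 11% discontinuation rate corresponds to rule 1. The 16% related-SAE rate corresponds to nothing, because rule 2 counts SAEs attributed to a different treatment.

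Discontinuation is an imperfect stand-in for serious toxicity here. Appendix 1 says that study drug is in general withheld for Grade 3 immune-mediated events, and it allows durvalumab to resume after, for example, Grade 3 colitis, rash or pancreatitis once stated conditions are met. An SAE that starts after the last durvalumab dose cannot be a discontinuation, although section 15.8 collects SAEs for up to 90 days after that dose. Patients with such events count under no rule unless they miss transplant or die.

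Safety is the trial's primary question. At stake is whether the remaining 20 of 30 patients are enrolled without a prespecified pause when related SAEs run well above the rate the plan itself chose as its reference.

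**Working it through.** The documents give no false-pause or detection probability for the interim rules, so there is no stated figure to reproduce. The check compares benchmarks with rules, then sizes the gap.

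**Benchmarks against rules (14.2 and 10.4)**

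- 11% discontinuation for treatment-related AEs: rule 1, direct match.
- 16% treatment-related SAEs: no match. Rule 2 counts locoregional SAEs. Rules 1, 3 and 4 pick up immunotherapy toxicity only through its consequences.

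**Timing**

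The look is at 10 patients enrolled (10.4). Five doses every 4 weeks put the last durvalumab dose at day 1 + 4 × 28 = 113. Locoregional therapy then comes no earlier than day 113 + 28 = 141, and transplant no earlier than day 113 + 72 = 185. For recently enrolled patients who complete dosing, rules 2 and 3 and the post-transplant part of rule 4 may not yet be assessable, which weakens the indirect capture.

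**Pause probabilities**

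For a rule of r or more out of 10 at true rate p, the exact binomial probability is

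P(X ≥ r) = 1 − Σ C(10,k) p^k (1−p)^(10−k), k = 0 to r−1.

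- Rule 1 at its own benchmark, p = 0.11, r = 3: 1 − (0.3118 + 0.3854 + 0.2144) = 0.088.
- Related-SAE count at p = 0.16, r = 3: 1 − (0.1749 + 0.3332 + 0.2856) = 0.206.
- The same with r = 4: subtract a further 0.1450, giving 0.061.

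SAE rates above 16% are assumptions. Rule 1 is shown under two assumptions: discontinuation stays at 11%, or it keeps the ratio 11/16 to the SAE rate (for example 32% × 11/16 = 22%).

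| True related-SAE rate | SAE count ≥3 of 10 | SAE count ≥4 of 10 | Rule 1, discontinuation 11% | Rule 1, discontinuation in proportion |
|---|---|---|---|---|
| 16% | 20.6% | 6.1% | 8.8% | 8.8% (at 11%) |
| 32% | 66.9% | 40.4% | 8.8% | 38.3% (at 22%) |
| 40% | 83.3% | 61.8% | 8.8% | 54.8% (at 27.5%) |
| 50% | 94.5% | 82.8% | 8.8% | 72.5% (at 34.4%) |

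**Chance that many SAEs leave rule 1 silent**

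Let s be the SAE rate and q the probability that a patient with an SAE discontinues, with discontinuation arising only through SAEs (assumed). Then

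P(≥3 SAE patients and <3 discontinuations) = Σ C(10,k) s^k (1−s)^(10−k) · P(Bin(k,q) ≤ 2), k = 3 to 10.

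At s = 0.32 this is 62.9% for q = 25%, 46.2% for q = 50%, and 28.6% for q = 69% (the ratio 11/16).

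**The case against.** A reader might infer that excess serious toxicity cannot trip any rule, or that the chance of a pause from related SAEs is zero at any true rate. The documents do not support that. Toxicity that ends immunotherapy counts under rule 1, toxicity that costs a transplant under rule 3, and a fatal event under rule 4. Appendix 1 requires permanent discontinuation for many severe events, including Grade 3-4 pneumonitis and nephritis and Grade 2 or higher myocarditis and encephalitis. Tremelimumab is given once and cannot be stopped later, but a tremelimumab-driven event that stops durvalumab still counts under rule 1.

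If discontinuation rises in proportion to SAEs, rule 1 already does much of the work: 38.3% at a 32% SAE rate, against 40.4% for a new rule of 4 or more. The gap is large only where SAEs and discontinuations come apart, and the documents do not say how often that would happen.

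The interim analysis also takes place whether or not a trigger is met, and the DSMB receives SAEs and can advise action. The 16% could serve as a descriptive comparator in that analysis, and saying so would remove the inconsistency in the text. However, 14.2 calls the figure a guardrail and says it will be used, and the board's discretion carries no number. These safeguards lessen the consequence but do not supply the promised check.

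The 18% related-SAE figure in section 15.4 might be read as support for the benchmark. It describes tremelimumab at 1 mg/kg, not the single 300 mg dose used here, so this point does not rely on it.

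**Conclusion.** The concern holds as a mismatch between what 14.2 promises and what the rules count. The plan names a 16% related-SAE guardrail and provides no rule that applies it. Related SAEs that are held and resumed, or that begin after the last durvalumab dose, go uncounted unless a missed transplant or death follows.

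The size is conditional. At an assumed 32% related-SAE rate, rule 1 pauses with probability between 8.8% (discontinuation unchanged at 11%) and 38.3% (discontinuation at 22%). Three or more of 10 patients would have a related SAE with probability 66.9%.

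These figures assume independent patients with a common rate and complete observation of all 10. At the moment the tenth patient enrols, observation will be incomplete, so pause probabilities at that moment would be lower for the existing rules and for any added one.

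**What to change.** In 10.4 and 14.2, add a fifth enrolment-pause rule. It should count patients among the first 10 treated who have an SAE at least possibly related to durvalumab and/or tremelimumab, from first dose and whether or not drug was stopped. State the period over which each patient is counted, and the rule's operating characteristics.

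The sponsor can choose between two thresholds:

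- **4 or more of 10:** pauses with probability 6.1% at 16%, 40.4% at 32% and 61.8% at 40%. It has fewer false pauses but misses a doubling of the rate about 60% of the time (100% − 40.4%).
- **3 or more of 10:** pauses with probability 20.6%, 66.9% and 83.3%. It matches the other rules and is more sensitive, with about a one-in-five false-pause chance at the benchmark.

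The cost is one sentence in each of two sections and a 6% to 21% chance of an unneeded pause if the true rate is 16%. No new data are needed, because section 15.8 already records seriousness and causality. The rule governs enrolment only and leaves every patient's treatment as it is.

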14.3. Analysis of Secondary Endpoints

For the secondary endpoint of death-censored graft loss, 2.5% of patients undergoing a liver transplant in these settings experience graft loss. If $\geq 7.5\%$ of patients in this study experience graft loss within 30 days of transplant, it will be considered a serious safety signal. For the efficacy endpoints, radiologic and pathologic response rates will be assessed as proportions, and overall and recurrence-free survival will be assessed using the Kaplan Meier method.

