6.6. Hepatocellular Carcinoma Background

Hepatocellular carcinoma (HCC) is an aggressive malignancy, developing most often in the setting of cirrhosis of the liver (Sohal et al Current Oncol Rep 2011; Gordan et al JCO 2020). For advanced disease, immunotherapy has now become standard of care – a combination of atezolizumab and bevacizumab has shown the best overall survival outcome so far (Finn et al NEJM 2020).

For earlier stage disease, however, there is no systemic therapy standard. The best treatment for HCC in the setting of cirrhosis is a liver transplant allowing potential cure for both the cancer and cirrhosis. Patients with HCC must meet institutional liver transplant criteria. Nonetheless, 25-35% of patients fail to reach liver transplant because of disease progression while waiting for a transplant (Sinha et al, Hepatology 2019) and approximately 15% experience HCC recurrence after transplant (Mehta et al, Transplantation 2020). Taken together, this constitutes a large subset of this patient population who cannot achieve a cure.

Given the success of immunotherapy in the advanced setting, it is imperative to study this in the pre-transplant setting, to improve the outcomes cited above. The major risk, of course, is graft

rejection by the primed immune system. Therefore, before a larger study may be conducted to assess efficacy of this approach, we will undertake this pilot trial to ensure safety – with the primary outcome focusing on acute cellular rejection of the transplanted liver.

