14. STATISTICAL CONSIDERATIONS

14.1. Study Design/Endpoints

The primary endpoint of safety is a binary endpoint, and will be assessed in patients undergoing liver transplant. Safety will be assessed using “treatment failure”, defined as rejection, graft loss, death, or loss to follow up within 30 days of transplant. Historically, 10-20% of patients are expected to experience acute cellular rejection within 30 days of transplant. We propose that an observed proportion of 20% failure will be a clear indicator of safety in this pilot study, whereas an observed proportion of 50% failure will be a clear indicator of failure. Using these guardrails, with at least 20 patients going to transplant, we will have 80.6% power to demonstrate a failure proportion of 20% (4 patients experiencing failure) versus a null of 50% (10 patients experiencing failure), with a one-sided alpha of 0.05. With 25 patients going to transplant, the power will increase to 86% (other parameters being the same).

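### The four pause rules count no rejection, graft loss or treatment failure (only death), and the 7.5% graft-loss line does not settle whether 2 or 3 events reach it

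*Combined protocol and SAP*

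**What the plan says.** Section 6.6 names graft rejection as the major risk and describes a pilot run to establish safety, "with the primary outcome focusing on acute cellular rejection of the transplanted liver". Section 14.1 defines the primary endpoint, treatment failure, as "rejection, graft loss, death, or loss to follow up within 30 days of transplant". It is assessed in transplanted patients; 20% observed failure is taken as clear evidence of safety and 50% as clear evidence of failure.

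Sections 10.4 and 14.2 list the same four triggers for halting enrollment, each at 3 or more of the first 10 patients:
- immunotherapy stopped for treatment-related adverse events;
- "patients experience SAEs related to locoregional therapy after immunotherapy";
- transplant not reached because of immunotherapy toxicity;
- deaths from enrollment to 30 days after transplant.

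The look is timed at 10 patients enrolled.

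On graft loss, 14.3 gives a background rate, "2.5% of patients undergoing a liver transplant in these settings experience graft loss", and then a line: if 7.5% or more "of patients in this study experience graft loss within 30 days of transplant, it will be considered a serious safety signal". The synopsis carries the same line. Neither place gives an event count, a time of assessment or a stated consequence. Section 14.2 plans 30 enrolled so that at least 20 reach transplant.

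The synopsis also says that the DSMB, the investigators, the sponsor-investigator and the drug company will consider modifying or ending the study if worrying safety findings arise, during the study and at the interim. Section 17.3 provides regular DSMB review.

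**The concern.** The plan puts numbers on four risks but none on rejection, its central one. Failures could accumulate toward the 50% that the plan itself regards as failure, and unless patients die no prespecified count would call for a review.

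The one numeric statement about the graft is worded on a different population from its own reference rate. Two readers with the same data could disagree on whether the signal has occurred.

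**Working it through.** **1. The plan's own figure.** Inputs from 14.1: n = 20, null 0.50, alternative 0.20, one-sided alpha 0.05. Exact binomial, declaring safety at 5 or fewer failures:
- alpha = P(X ≤ 5 | 0.50) = 0.0207 (a cut of 6 gives 0.0577, above 0.05);
- power = P(X ≤ 5 | 0.20) = 0.8042, against 80.6% stated.

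This reproduces closely enough to serve as the base for step 5.

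**2. What the pause rules count.**

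| Component of treatment failure | Counted by a pause rule? |
|---|---|
| Rejection | No |
| Graft loss | No |
| Death within 30 days of transplant | Yes, fourth rule |
| Loss to follow-up | No |
| The composite | No |

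Ten non-fatal rejections in the first 10 patients would trip none of the four rules.

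Timing adds to this. Five doses every 4 weeks put the last dose at 4 × 28 = 112 days. With the 72-day minimum gap, transplant is no earlier than day 184, and 30-day data no earlier than day 214. Assuming uniform accrual of 30 patients over four years and all five doses given, 30/4 × 214/365.25 ≈ 4.4 patients enroll in 214 days. So about 4 of the first 10 could have no 30-day graft outcome when the tenth enrolls, before any waiting-list time.

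**3. Events needed to reach 7.5%.** This is the smallest k with k/n ≥ 0.075. Since 0.075 × 13 = 0.975, 0.075 × 14 = 1.05, 0.075 × 26 = 1.95 and 0.075 × 27 = 2.025:
- 1 event for n up to 13;
- 2 events for n = 14 to 26;
- 3 events for n = 27 to 30.

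Two losses are 2/20 = 10.0% or 2/26 = 7.7% of transplants (signal), but 2/30 = 6.7% of enrolled patients (no signal).

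**4. Chance of a signal with 20 transplants.** On transplants, P(X ≥ 2) = 1 − (1−p)^20 − 20p(1−p)^19. On 30 enrolled, P(X ≥ 3) subtracts a further 190p²(1−p)^18. At p = 0.075: 1 − 0.2103 − 0.3410 = 0.449, and 0.449 − 0.263 = 0.186.

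| True graft-loss rate | 2 needed (of 20 transplanted) | 3 needed (of 30 enrolled) |
|---|---|---|
| 2.5% | 8.8% | 1.3% |
| 7.5% | 44.9% | 18.6% |
| 10% | 60.8% | 32.3% |
| 15% | 82.4% | 59.5% |

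**5. What a review count on treatment failure could do (illustration only).** Count failures in order of transplant and review at 3 or more of the first 5, 5 of 10 or 7 of 15. Exact enumeration of first crossings:
- true 50%: 0.500 + 0.187 + 0.097 = 0.784;
- true 20%: 0.058 + 0.015 + 0.005 = 0.078.

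If every crossing ended the trial, power would fall from 80.4% to 78.1% and alpha from 2.07% to 1.93%. A non-binding rule costs less. The average number of transplants at a true 50% would be about 10 (0.500×5 + 0.187×10 + 0.097×15 + 0.216×20 = 10.1), but only if transplants stopped at once.

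**The case against.** A reader might infer that graft harm is unmonitored and that nothing follows from the signal. The documents do not support that. The synopsis has safety signals considered by the DSMB and others throughout the study, and 14.3 labels 7.5% graft loss as such a signal. Section 17.3 gives the DSMB a narrative on trends and safety events, 15.14 sends SAEs to it regardless of causality, and the fourth rule counts deaths. What is missing is a prespecified count and an explicit link.

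The general channel is also thin at this point. Section 15.8 ends routine adverse-event collection at the latest 90 days after the last dose, and transplant is at least 72 days after it. That covers at most 90 − 72 = 18 of the 30 post-transplant days, apart from late-onset events attributed to study drug. Rejection data are collected separately, but the list of DSMB report contents in 17.3 names neither rejection nor graft loss.

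A reader might also infer that the plan means to divide graft losses by enrolled patients. That is the literal wording but the less natural reading: loss within 30 days of transplant can occur only in transplanted patients, and both the reference rate and the primary endpoint use them. On transplants, 3 events are needed only at 27 or more of 30. If 25% fail to reach transplant, the low end of the range in 6.6, that has probability of about 3.7%. The contrasts in step 4 therefore measure an ambiguity, not an established error.

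Finally, the average of 10 transplants should not be read as a halving of exposure. The pause in 10.4 and 14.2 halts enrollment only, and patients already treated would go on toward transplant.

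**Conclusion.** The concern holds in two parts. No numeric pause rule covers rejection, graft loss or the composite primary endpoint; death is the only component counted, and the rest depends on judgement. And the 7.5% line is ambiguous between 2 and 3 events whenever 20 to 26 of 30 patients are transplanted, which with 20 transplants moves the chance of a signal from 44.9% to 18.6% at a true 7.5%. Even on the more sensitive reading, a true rate at the line is missed 55% of the time.

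The figures assume independent patients with a common event rate and all 30 enrolled. The timing figure also assumes uniform accrual and five doses. Because general oversight exists and the transplanted denominator is probably intended, this is a should-fix.

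**What to change.** 1. **Synopsis and 14.3.** State that the 7.5% line applies to transplanted patients. Give the matching counts (1 event up to 13 transplants, 2 for 14 to 26, 3 for 27 to 30) or a fixed time of analysis. Link the signal explicitly to the review already described in the synopsis. If a single early event is not meant to prompt review, say so: a flat count of 2 would loosen the plan's own line below 14 transplants, where 1 of 10 is already 10%.
2. **10.4 and 14.2.** Add a non-binding review trigger on treatment failure, counted in order of transplant. The sponsor and DSMB should set the count and state its operating characteristics; the 3 of 5, 5 of 10, 7 of 15 boundary is only an example.
3. **17.3.** Add rejection and graft-loss counts, with the number transplanted, to the DSMB report.

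The cost is protocol wording and prompt entry of the 30-day rejection data. Graft liver tests are already at least weekly, but rejection data are scheduled at 30 days, 3 months and 6 months. Under the example boundary there is about an 8% chance of an unneeded review at a true 20% failure rate, and power falls by at most 2.3 points (80.4 − 78.1).
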